10.2 Study Suspension or Termination

The sponsor may suspend or terminate the study or part of the study at any time for any reason. Should this be necessary, subjects should be seen as soon as possible and treated as described in [Section 9.3](#) for prematurely withdrawn subjects. The investigator may be informed of additional procedures to be followed in order to ensure that adequate consideration is given to the protection of the subject's interests. The investigator will be responsible for informing Institutional Review Boards (IRBs) and/or Ethics Committees (ECs) of the early termination of the study.

If the investigator suspends or prematurely terminates their participation in the study, the investigator will promptly inform the sponsor and the IRB/IEC/REB and provide them with a detailed written explanation. Subjects should be seen as soon as possible and treated as described in [Section 9.3](#) for prematurely withdrawn subjects. The investigator will also return all test articles, containers, and other study materials to the sponsor.

11 QUALITY CONTROL AND ASSURANCE

The sponsor performs quality control and assurance checks on all clinical studies that it sponsors. Before enrolling any subjects in this study, sponsor personnel and the investigator review the protocol, the Investigator's Brochure, the case report forms (CRFs) and instructions for their completion, the procedure for obtaining informed consent, and the procedure for reporting AEs and SAEs. A qualified representative of the sponsor monitors the conduct of the study by visiting the site and by contacting the site by telephone and e-mail. During these site visits, information recorded in the CRFs is verified against source documents.

12 PLANNED STATISTICAL METHODS

12.1 General Considerations

All analyses of data for this study will comply with International Conference on Harmonisation (ICH) of Technical Requirements for Registration of Pharmaceuticals for Human Use (ICH-E9) and the sponsor's guidance documents and standards. Statistical analyses will be performed using Statistical Analysis Software (SAS®).

A Statistical Analysis Plan incorporating the sections below and with mock table, figure, and listing (TFL) shells will be prepared, approved and finalized by the sponsor prior to database lock. This plan will define populations for analysis, outline all data handling conventions, and specify statistical methods to be used for analysis of safety and efficacy. Analyses of PK endpoints will be described in a separate analysis plan.

Descriptive statistics, including the numbers and percentages for categorical variables, and the numbers, means, standard deviation (SD), medians, minimums, and maximums for continuous variables will be provided. Exploratory analyses may also be performed. Listings of individual subject's data will be produced.

All eCRFs must be completed, entered and checked; all safety laboratory results must have been reported; all AEs must have been fully characterized (eg, relationship to test article determined) and coded; and all queries must have been resolved prior to database lock and unblinding. Determination of inclusion in the analysis populations, characterization of protocol deviations as major/minor and final approval of the SAP will also be completed prior to database lock.

12.2 Determination of Sample Size

Enrollment of a total of approximately 225 subjects is planned. The Bayesian posterior probability that the clinical success rate at the PTE Visit is within 0.10 of that of the nitrofurantoin group will be estimated for each omadacycline dose group. The target probability is 0.80. If the true underlying clinical success rates for the nitrofurantoin and omadacycline dose groups are 0.82, then the sample size of $N = 50$ per treatment has approximately 79% power/probability to yield the target probability ($N = 53$ per treatment for 80% power). The sample size may be increased for a particular omadacycline dose group by changing the randomization ratio and/or dropping a dose group to achieve improved power/probability of achieving the target probability that clinical success rates for a dose group is within 0.10 of that of the nitrofurantoin group. If required to improve the precision of the interim or projected final analyses estimates of response rates or posterior probabilities, sample size may be increased to a maximum sample size provided in the SAP.

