7.2 Primary Efficacy Endpoint Analysis

The primary efficacy endpoint is investigator's assessment of clinical response at PTE in the ITT population, as measured by the number of subjects in each treatment group.

The primary efficacy outcome is the percentage of subjects with an overall clinical success at the PTE Assessment in the ITT population. Each omadacycline treatment group will be compared to nitrofurantoin group for non-inferiority (pairwise). This non-inferiority test will be based on the lower limit of the 2-sided exact 95% confidence interval (CI).

The null and alternative hypotheses are as follows for overall clinical success:

$$H_0 : p_1 - p_2 \leq -\Delta \text{ and } H_1 : p_1 - p_2 > -\Delta,$$

where p_1 is the primary efficacy success rate in each of the omadacycline treatment group, p_2 is the primary efficacy success rate of nitrofurantoin group, and Δ is the non-inferiority margin of 10%. No multiplicity adjustment will be used to account for multiple doses being compared to levofloxacin.

To test the null hypothesis, a 2-sided 95% CI for the observed difference in primary outcome rates (omadacycline group minus nitrofurantoin group) will be calculated. If the lower limit of the 95% CI for the difference exceeds -10% , then the null hypothesis will be rejected and the non-inferiority of omadacycline to nitrofurantoin will be declared for that dose.

The number and percentage of subjects in each treatment group defined as an overall clinical success, failure and indeterminate (subjects with missing data or who are lost to follow-up) will be tabulated, as will the overall category combining failure and indeterminate.

In addition, 95% credible intervals will be provided for the difference in success rates using the modeling as follows. Assuming the likelihood for number of responders to have binomial distribution [$Y_i \sim \text{Bin}(n_i, p_i)$] and non-informative beta priors [$p_i \sim \text{Beta}(0.5, 0.5)$]. The posterior probability of non-inferiority will be computed as $P(p_{\text{OMC}} - p_{\text{N}} > -0.1 \mid \text{data})$ for assessment.

Additional sensitivity analyses are described in [Section 7.5.2](#).

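### At the stated 0.80 target the power is about 69% at 50 per arm and about 70% at 53, not the stated 79% and 80%

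*Protocol*

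**What the plan says.** Protocol 12.2 bases the sample size on "The Bayesian posterior probability that the clinical success rate at the PTE Visit is within 0.10 of that of the nitrofurantoin group", evaluated for each omadacycline dose group. It then fixes the threshold: "The target probability is 0.80". The power claim is conditional: "If the true underlying clinical success rates for the nitrofurantoin and omadacycline dose groups are 0.82", then 50 subjects "per treatment has approximately 79% power/probability to yield the target probability", with 53 "per treatment for 80% power". The Synopsis (Statistical Methods) and SAP 3.1 repeat the same figures.

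The power sentence names no prior and no formula. Protocol 12.5.1 says the comparison of each dose with nitrofurantoin uses a beta distribution with an uninformative prior. SAP 7.2 gives the detail. For the likelihood: "Assuming the likelihood for number of responders to have binomial distribution". The prior is Beta(0.5, 0.5) in each arm. For the criterion: "The posterior probability of non-inferiority will be computed as" the one-sided probability, given the data, that the omadacycline rate minus the nitrofurantoin rate exceeds -0.1.

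**The concern.** A power figure that states its threshold, margin, true rates and arm size can be recomputed. This one comes out about 10 points lower than printed, which is too large a gap for rounding or for the word approximately.

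It is the only quantitative justification of arm size in either document. The Amendment 2 summary of changes gives at least 53 per arm as the initial goal. A reader who trusts 79% will take a missed 0.80 as stronger evidence against a dose than it is.

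The consequence should not be overstated. Missing the target does not drop a dose: Protocol 12.7 ties possible stopping to a probability below 30%. SAP 7.2 rests the final non-inferiority decision on the 95% confidence interval.

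**Working it through.** **Inputs**

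| Input | Value | Source |
|---|---|---|
| Target posterior probability, t | 0.80 | Protocol 12.2 |
| Margin | 0.10 | Protocol 12.2; SAP 7.2 |
| True success rates | 0.82 in both arms | Protocol 12.2 |
| Arm size and stated power | 50 gives 79%; 53 gives 80% | Protocol 12.2 |
| Likelihood and prior | binomial; Beta(0.5, 0.5) per arm | SAP 7.2 |
| Criterion | P(pOMC - pN > -0.10 given data) | SAP 7.2 |

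Using the SAP 7.2 prior for the power sentence is an assumption, tested below.

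**Exact calculation.** For each pair of success counts (y1, y2) from n per arm, the posteriors are Beta(0.5 + y, 0.5 + n - y). The posterior probability of non-inferiority comes from numerical integration. Power is the sum of Bin(y1; n, 0.82) x Bin(y2; n, 0.82) over all pairs where that probability is at least 0.80.

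| Prior (both arms) | n = 50 | n = 53 |
|---|---|---|
| Beta(0.5, 0.5) | 69.2% | 69.5% |
| Beta(1, 1) | 69.2% | 71.2% |
| Beta(1/3, 1/3) | 69.2% | 69.5% |
| Beta(0.01, 0.01) | 67.4% | 69.6% |
| Stated | 79% | 80% |

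**Check by hand.** With a normal approximation, power = Phi(0.10/SE - 0.8416), where SE = sqrt(2 x 0.82 x 0.18 / n).

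- n = 50: SE = 0.0768; 0.10/SE = 1.301; Phi(0.460) = 67.7%.
- n = 53: SE = 0.0746; 0.10/SE = 1.340; Phi(0.498) = 69.1%.

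A simulation of 4,000 trials gives 69.0% and 69.2%.

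**Attempts to reach the stated pair**

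| Reading | n = 50 | n = 53 |
|---|---|---|
| Two-sided, absolute difference below 0.10, t = 0.80 | 19.5% | 24.0% |
| Average posterior probability | 82.7% | 83.4% |
| Observed difference within 0.10 either way | 84.9% | 83.7% |
| Control rate treated as known, Beta(0.5, 0.5) | 82.3% | 85.5% |
| One-sided, t = 0.71 | 78.3% | 80.5% |
| One-sided, t = 0.70 | 79.8% | 81.2% |

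No reading tried at t = 0.80 gives both figures. A threshold of 0.70 to 0.71 comes close, but those values were found by working backwards and do not establish the cause.

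**Arm size for 80% power at t = 0.80, Beta(0.5, 0.5).** The exact power is 79.6% at 80 per arm and 80.2% at 81. Five arms of 81 make 405 subjects, above the maximum of 300 in SAP 3.1. An equal split of the planned total is 225/5 = 45 per arm, where the power is 66.7%. That split is an illustration only, because allocation is adaptive and Group 4 joined late.

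**The case against.** The strongest objection is that the generating model may not be in these documents. SAP 3.1 places the decision-rule statistics in a separate DMC SAP, and Protocol 12.5.1 mentions further Bayesian modelling without detail. A model that borrows information across dose groups would raise the figure. As an upper illustration, pooling three equal omadacycline arms against one control at the 0.80 target gives 81.0% at 50 per arm and 82.7% at 53, so partial borrowing could land near 79%.

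This does not rescue the text. Neither document mentions borrowing in connection with the power claim. Protocol 12.2 speaks of each dose group, and Protocol 12.5.1 describes a group-by-group beta comparison with an uninformative prior. What stands is that 69% and 70% are conditional on the SAP 7.2 model.

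A second objection concerns importance. This is an exploratory Phase 2 trial with adaptive allocation, discretionary stopping, a total that may rise to 300 and a final decision based on a confidence interval. The error therefore biases no analysis. That is correct and limits the harm to planning and interpretation. It does not make the figure right, and the gap between 53 and 81 per arm is material to planning.

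**Conclusion.** The stated power is wrong as written. With the stated target, margin and true rates, and the SAP 7.2 model, the chance of reaching 0.80 is 69.2% at 50 per arm and 69.5% at 53, so the plan overstates it by about 10 points (79 - 69.2 = 9.8; 80 - 69.5 = 10.5). The chance that an equally effective dose misses the target at 50 per arm is 100 - 69.2 = 30.8%, against the implied 21%.

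The result assumes independent arms, fixed and equal arm sizes, the one-sided criterion and an uninformative prior. The choice among the four priors tried does not close the gap, and a literal two-sided reading widens it. Confidence is high that 79% and 80% do not follow from the stated inputs; why they were printed is unknown.

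**What to change.** In the Synopsis, Protocol 12.2 and SAP 3.1, restate the power at the 0.80 target as about 69% for 50 per arm and about 70% for 53, and name the prior and the one-sided criterion used. This is a text correction. It makes the stated power less favourable and changes no endpoint, threshold or analysis.

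Alternatively, if the figures came from a different target, prior or model, state it. That route may cost more: a target other than 0.80 would no longer match the 80% expansion threshold in Protocol 5.1.1 and 12.7, and the two would need to be reconciled.

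Two secondary points can be handled in the same edit:

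- Replace the loose wording about being within 0.10 with P(pOMC - pN > -0.10 given data), as in SAP 7.2. The parallel within-10% wording in the Synopsis adaptive-design text and in Protocol 5.1.1 and 12.7 should follow.
- If a power figure for the planned 225 is wanted, compute it at projected arm sizes. Protocol 7.4 cites blinded data on the first 145 subjects in its rationale for adding Group 4, so equal arms cannot be assumed.

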12.3 Analysis Populations

The following subject analysis populations have been defined:

- Intent-to-treat (ITT): all randomized subjects.

- Safety: all randomized subjects who receive any amount of test article.
- The microbiological ITT (micro-ITT) population will consist of subjects in the ITT population who have a study-qualifying pre-treatment Baseline urine culture with 1 or 2 uropathogens at $\geq 10^5$ CFU/mL.
- The clinically evaluable (CE) population will consist of all ITT subjects who received test article, have a qualifying infection, an assessment of outcome, and meet all other evaluability criteria detailed in the SAP
- The microbiologically evaluable (ME) population will include subjects in the CE population who have a study-qualifying pre-treatment Baseline urine culture with 1 or 2 uropathogens at $\geq 10^5$ CFU/mL.

12.4 Demographics and Baseline Characteristics

Demographics (including age, ethnicity and race) and Baseline characteristics will be summarized in the ITT population by treatment group.

Descriptive statistics of the duration of test article treatment will be provided by treatment group. The number and percentage of subjects who prematurely discontinued test article and the reason for discontinuation and the number and percentage of subjects prematurely discontinuing the study and the primary reason for discontinuation will be presented by treatment group.

12.5 Primary Endpoint(s)

12.5.1 Efficacy Endpoint

The primary efficacy endpoint is the Investigator's assessment of clinical success at PTE in the ITT population. The number and percentage of subjects with an Investigator's assessment of clinical success, clinical failure and indeterminate response at the PTE visit will be determined by treatment group in the ITT population. Exact 95% confidence intervals will be determined for the point estimates of the clinical success rates in each treatment group.

A comparison of the clinical success rate at the PTE Visit between each omadacycline dose group and the nitrofurantoin group will be conducted using a beta distribution with an uninformative Bayesian prior distribution. Additional analyses on the primary efficacy endpoint will be performed using Bayesian modeling. Details are described in SAP.

12.6 Secondary Endpoint(s)

12.6.1 Safety Endpoint(s)

All safety analyses will utilize the Safety population. Summary tables will be provided for all treatment-emergent adverse events (TEAEs). A TEAE is defined as an AE with a start date and time on or after the first dose of test article. AEs will be coded using the Medical Dictionary for Regulatory Activities (MedDRA) and will be summarized by presenting the number and percentage of subjects having each TEAE for each treatment group by system

organ class (SOC) and preferred term (PT), by SOC, PT and severity, and by SOC, PT and relationship to test article. Additional tabulations will provide summaries by SOC and PT of subjects experiencing SAEs and TEAEs judged to be related to test article.

The following variables will be analyzed descriptively by treatment group in the Safety population:

- Vital signs (systolic and diastolic BP, heart rate, body temperature), including change from Baseline by visit and time point measured
- Clinically notable vital signs (meeting predefined criteria as specified in the SAP) by visit and time point measured
- Laboratory parameters, including change from Baseline by visit
- Clinically notable laboratory parameters (meeting predefined criteria as specified in the SAP) by visit

12.6.2 Efficacy Endpoint(s)

The number and percentage of subjects with an Investigator's assessment of clinical success, clinical failure and indeterminate response at the EOT Visit (ITT and CE populations; by definition subjects in the CE population cannot have an indeterminate response) and PTE visit (CE and micro-ITT population) will be determined by treatment group. Exact 95% confidence intervals will be determined for the point estimates of the clinical success rates in each treatment group.

The number and percentage of subjects with a microbiologic failure, success and indeterminate response at the EOT and PTE Visits (micro-ITT and ME populations; by definition subjects in the ME population cannot have an indeterminate response) will be determined by treatment group. Exact 95% confidence intervals will be determined for the point estimates of the microbiologic success rates in each treatment group.

12.7 Interim Analysis

This is an adaptive dose-response finding study. Bayesian analysis will be conducted when primary efficacy endpoint data (investigator assessment of clinical response at PTE) is available from 40, 80 and 100 subjects in order to:

- Determine if omadacycline dose group(s) that can be dropped from the trial, or
- Modify the randomization ratios among the omadacycline dose groups to improve the precision of the selected dose group comparison of clinical success to that of the nitrofurantoin group.

Additional analyses may be carried out for these same two purposes. Response criteria are targeted toward estimating the probability that the clinical success rate (proportion of subjects) for each dose group is within 10% of that of the nitrofurantoin group. If at the specified analysis time point, that probability falls below 30% for a particular omadacycline dose group, recruitment for that omadacycline dose group may be stopped or curtailed by changing the randomization ratio. If that probability exceeds 80% for a particular

omadacycline dose group, recruitment for that dose group may be increased by changing the randomization ratio to improve the precision of the estimate.

Results from the Bayesian analysis will be reviewed by a DMC to determine if enrollment in any omadacycline treatment arms should be stopped or modified. Modifications to omadacycline dosing regimens/treatment arms may also be based on safety and tolerability. A DMC charter describing the composition of the DMC, roles and responsibilities, and statistical parameters will be developed and finalized prior to the first data review.

12.8 Data Monitoring Committee

A DMC will provide ongoing monitoring of data. The charter for the DMC will clearly outline membership, all roles, responsibilities, and decision-making criteria. This will include a detailed description of the manner in which security and blinding of the data for the study management team will be maintained, in addition to the procedures that ensure the independence and objectivity of the DMC's activities. As the DMC will be reviewing data for this study, it may require reports indicating treatment assignment to assist in clinical interpretation of its findings. Therefore, the DMC charter will provide a detailed explanation of the processes by which the DMC will obtain the information necessary for its operation that will not prejudice or create any potential source of bias in the conduct of the study.

13 ADMINISTRATIVE CONSIDERATIONS

13.1 Investigators and Study Administrative Structure

The investigator will permit study-related monitoring, audits, IRB/IEC/REB review, and regulatory inspections by providing direct access to source data and documents.

All information will be recorded on source documents. All required data will be recorded in the eCRFs.

If an investigator retires, relocates, or otherwise withdraws from conducting the study, the investigator must notify the sponsor to agree upon an acceptable storage solution. Regulatory agencies will be notified with the appropriate documentation.

An updated form 1572 will be filed with the sponsor for any changes in the study personnel reported in the current form 1572.

13.2 Institutional Review Board (IRB) or Independent Ethics Committee (IEC) Approval

The protocol and the proposed ICF must be reviewed and approved by a properly constituted IRB/IEC/REB before study start. A signed and dated statement that the protocol and ICF have been approved by the IRB/IEC/REB must be given to the sponsor before study initiation. Prior to study start, the investigator is required to sign a protocol signature page confirming his/her agreement to conduct the study in accordance with these documents and all of the instructions and procedures found in this protocol and to give access to all relevant data and records to the sponsor monitors, auditors, designated agents of the sponsor, IRBs/IECs/REBs, and regulatory authorities as required. If an inspection of the clinical site is requested by a regulatory authority, the investigator must inform the sponsor immediately that this request has been made.

13.3 Ethical Conduct of the Study

This clinical study was designed and shall be implemented and reported in accordance with the ICH Harmonized Tripartite Guidelines for Good Clinical Practice (GCP), with applicable local regulations (including European Directive 2001/20/EC, US 21 Code of Federal Regulations (CFR), and Japanese Ministry of Health, Labor, and Welfare), and with the ethical principles laid down in the Declaration of Helsinki.

13.4 Patient Information and Consent

The investigator will provide for the protection of the subjects by following all applicable regulations. These regulations are available upon request from the sponsor. The ICF must be reviewed by the sponsor and approved by the IRB/IEC/REB.

Before any procedures specified in the protocol are performed, a subject must:

- Be informed of all pertinent aspects of the study and all elements of informed consent;

- Be given time to ask questions and time to consider the decision to participate;
- Voluntarily agree to participate in the study;
- Sign and date an IRB/IEC/REB-approved ICF.

13.5 Direct Access, Data Handling, and Record Keeping

13.5.1 Investigator

The investigator will permit study-related monitoring, audits, IRB/IEC/REB review, and regulatory inspections by providing direct access to source data and documents.

All information will be recorded on source documents. All required data will be recorded in the eCRFs.

If an investigator retires, relocates, or otherwise withdraws from conducting the study, the investigator must notify the sponsor to agree upon an acceptable storage solution. Regulatory agencies will be notified with the appropriate documentation.

An updated form 1572 will be filed with the sponsor for any changes in the study personnel reported in the current form 1572.

